8.2.4. Visit 6: Follow-up visit

The follow-up visit will be completed via remote video call (or phone call if video incapability) 7-14 days after the final dosing visit. Participants will be asked to report any adverse events. Female participants of childbearing potential will be asked to confirm the result of a urine pregnancy test completed on that day, previously provided by the research team on the last dosing visit.

8.2.5. Experimental visits for Stage 2:

The number of experimental visits in Stage 2 will depend on which treatment arms continue for further evaluation, based on the results of Stage 1. A minimum of 36 hours will be maintained between visits. The specific details of Stage 2 experimental visits will be determined after analysis of Stage 1 data and according to the criteria outlined in Section 5.4.

8.3. Laboratory Tests

At the screening visit, a blood sample will be taken from each participant to test for haematology (FBC) renal function (urea and electrolytes) and hepatic function (liver function tests). A urine sample will also be taken for Urinalysis. These tests will be completed by the study team and be processed according to standard local procedures.

Table 6 Laboratory Tests

Full Blood	Count (FBC)	Liver Function Tests (LFTs)	Urea & Electrolytes (U&Es)	Urinalysis
White Blood Cell count	Lymphocyte Count	Total Protein	Sodium	Protein
Red Blood Cell count	Monocyte Count	Total Bilirubin,	Potassium	Blood
Haemoglobin	Eosinophil Count	ALP	Creatinine	Leucocytes
Haematocrit	Basophils	AST	Urea	Nitrate
Mean Cell Volume	Immature Granulocytes Count	GGT		Glucose
Mean Cell Concentration	Metamyelocytes Count	Albumin		Ketone
Red Cell Distribution Width	Myelocytes Count	Globulin		рН
Mean Cell Haemoglobin Concentration	Promyelocytes Count			Specific gravity
Platelet Count	Blasts Count			Bilirubin
Mean Platelet Volume	Nucleated RBC's			Urobilinogen
Neutrophil Count				

Urine samples for urinalysis, drug and pregnancy testing will be collected in standard collection pots. The samples will be disposed of as soon as the tests are successfully completed.

On day one of each experimental visit, participants will have a venous cannula inserted for the collection of blood samples. Blood samples will be collected in 5ml EDTA tubes.

Total blood volume collected per participant will not exceed 100ml for the study.

Within 30 min of collection, the samples will be centrifuged (3000rpm for 10min). The plasma will be decanted from the tube into two screw-cap collection tubes and immediately placed in a -20°C freezer in the CRF. The stored samples will be pseudo-anonymised with participant ID, visit number and time point. Only the research team will be able to link the ID number to the participant's details. At the end of each day, the sample will be moved to a -80°C freezer for longer-term storage in the King's CRF.

Only plasma will be stored so that analyses can be completed. No human tissue will be stored at the end of the research. Biological samples collected from participants as part of this trial will be transported, stored, accessed, and processed in accordance with the 2004 Human Tissue Act.

PK blood samples will be analysed at a KCL laboratory, Department of Nutritional Sciences. All other samples will be analysed either at the CRF or Synnovis, Kings College Hospital.

9. Assessment of Efficacy

9.1. Efficacy Parameters

9.1.1. Primary Efficacy Parameters

The primary efficacy parameter for this study is t_{max} .

9.1.2. Secondary Efficacy Parameters

- a) Pharmacokinetic Parameters:
 - Time to 50% of maximum concentration (T50%)
 - Maximum Plasma Concentration (Cmax)
 - Elimination Half-life (T1/2)
 - Area Under the Curve (AUC) from:
 - Time zero to 15 minutes (AUC₀₋₁₅)
 - o Time zero to infinity (AUC_{inf})
- b) Local Tolerability:
 - Buccal and Sublingual Wafer Disintegration
 - Visual Analogue Scale (VAS) for Taste and Tolerability

9.2. Procedures for Assessing Efficacy Parameters

The following procedures will be used to assess the efficacy parameters:

Blood Sampling:

- Venous blood samples (1 mL) will be collected via IV cannulation at the following time points for each formulation: 0 (pre-dose), 2, 4, 6, 8, 10, 12.5, 15, 30 and 45 minutes and 1, 1.5, 2, 4 hours after dosing. Each sample will be split into two plasma cryovials.
- Samples will be centrifuged within 30 minutes of collection, and plasma will be separated and stored at -20°C until the end of the visit, and then stored at -80°C until analysis.

Plasma Naloxone Analysis:

- Plasma concentrations of naloxone will be determined using a validated liquid chromatography-tandem mass spectrometry (LC-MS/MS) method.
- The following parameter will be recorded in the eCRF for each time point: plasma naloxone concentration (ng/mL).

Pharmacokinetic Analysis:

- AUC will be calculated using the linear trapezoidal method and extrapolated to infinity.
- C_{max} and T_{max} will be determined directly from the observed concentration-time data.
- t1/2 will be calculated using the terminal elimination rate constant.
- Relative bioavailability will be calculated by comparing the dose-normalized AUC0-∞ of buccal and sublingual naloxone to that of IM and IN formulations.

Buccal and Sublingual Wafer Disintegration:

- The time for complete disintegration of the buccal naloxone wafer will be measured and recorded by a study team member.
- Participants will be asked to report the moment they feel the wafer has completely disintegrated.
- The following will be recorded in the CRF: time to complete disintegration (seconds).

Visual Analogue Scale (VAS) for Taste and Tolerability:

- Participants will complete a 100mm VAS immediately after administration of each formulation to assess taste and local tolerability.
- The following will be recorded in the CRF: VAS score for taste (0-100), VAS score for tolerability (0-100).

All efficacy assessments will be conducted for each of the three formulations (buccal/sublingual, IM, and IN) and for each dose of the buccal formulation (2mg and 4mg). The data collected will be used to construct individual plasma concentration-time profiles, calculate pharmacokinetic parameters, and compare the efficacy of the buccal and sublingual naloxone formulation to the existing IM and IN formulations.

These procedures will provide comprehensive data to assess the efficacy of the novel buccal and sublingual naloxone formulation in terms of its pharmacokinetic profile, bioavailability, and user acceptability compared to existing naloxone formulations.

10. Assessment of Safety

10.1. Specification, Timing and Recording of Safety Parameters

The safety of participants will be monitored throughout the study using a combination of physical examinations, laboratory tests, and adverse event reporting. These safety assessments are designed to detect any potential adverse effects and to ensure participant well-being throughout the study.

The trial will take place at the CRF at King's College Hospital. This facility is equipped with emergency resuscitation services, ensuring enhanced safety for participants in case of any adverse events or emergencies.

Laboratory Tests: The following laboratory tests will be performed at screening:

- > Full Blood Count (FBC): to assess overall health and detect any haematological abnormalities
 - 1. White Blood Cell count
 - 2. Red Blood Cell count
 - 3. Haemoglobin
 - 4. Haematocrit
 - 5. Mean Cell Volume
 - 6. Mean Cell Concentration
 - 7. Red Cell Distribution Width
 - 8. Mean Cell Haemoglobin Concentration
 - 9. Platelet Count
 - 10. Mean Platelet Volume
 - 11. Neutrophil Count
 - 12. Lymphocyte Count
 - 13. Monocyte Count

- 14. Eosinophil Count
- 15. Basophils
- 16. Immature Granulocytes
 Count
- 17. Metamyelocytes Count
- 18. Myelocytes Count
- 19. Promyelocytes Count
- 20. Blasts Count
- 21. Nucleated RBC's

- Liver Function Tests (LFTs): total protein, total bilirubin, AST, ALT, GGT, albumin and globulin to monitor for any hepatotoxicity
- Renal Function Tests (U&Es): Urea, creatine and Electrolytes (sodium and potassium) to assess kidney function
- ➤ Urinalysis: protein, blood, leucocytes, nitrate, glucose, ketone, pH, specific gravity, bilirubin and urobilinogen to screen for urinary tract infections or other abnormalities

Additional tests will be performed at the following time points:

- Pregnancy test for female participants: at screening, before each dosing session, and at the final follow-up visit
- Urine drug screen: at screening and before each dosing session

Special Considerations:

As buccal administration may cause local irritation, the oral mucosa will be examined before and at four hours after each dose administration, with any changes documented via the use of photography if necessary. IM injection site and nasal cavities will be examined in the other trial arms.

10.2. Procedures for Recording and Reporting Adverse Events

The Medicines for Human Use (Clinical Trials) Regulations 2004 and Amended Regulations 2006 gives the following definitions:

- Adverse Event (AE): Any untoward medical occurrence in a participant to whom a
 medicinal product has been administered, including occurrences which are not
 necessarily caused by or related to that product.
- Adverse Reaction (AR): Any untoward and unintended response in a participant to an
 investigational medicinal product which is related to any dose administered to that
 participant.
- Unexpected Adverse Reaction (UAR): An adverse reaction the nature and severity of which is not consistent with the information about the medicinal product in question set out in the reference safety information from:

The summary of product characteristics (SmPC) for that product (for products with a marketing authorisation)

The Investigator's Brochure (IB) relating to the trial in question (for any other investigational product)

- Serious adverse Event (SAE), Serious Adverse Reaction (SAR) or Suspected Unexpected Serious Adverse Reaction (SUSAR): Any adverse event, adverse reaction or unexpected adverse reaction, respectively, that:
 - results in death;
 - is life-threatening:
 - o required hospitalisation or prolongation of existing hospitalisation;
 - results in persistent or significant disability or incapacity;
 - o consists of a congenital anomaly or birth defect.
- Important Medical Events (IME) & Pregnancy: Events that may not be immediately

life-threatening or result in death or hospitalisation but may jeopardise the participant or may require intervention to prevent one of the other outcomes listed in the definition above should also be considered serious. Although not a serious adverse event, any unplanned pregnancy will also be reported via the SAE reporting system.

10.2.1. Reporting Responsibilities

KCL and SLaM have delegated the delivery of the Sponsor's responsibility for Pharmacovigilance (as defined in Regulation 5 of the Medicines for Human Use (Clinical Trials) Regulations 2004 to the King's Health Partners Clinical Trials Office (KHP-CTO).

All SAEs, SARs and SUSARs will be reported immediately by the Chief Investigator (and certainly no later than 24hrs) to the KHP-CTO and Sponsor R&D office in accordance with the current Pharmacovigilance Policy.

The KHP-CTO will report SUSARs to the relevant ethics committee and the regulatory authority MHRA.

Reporting timelines are as follows:

- SUSARs which are fatal or life-threatening must be reported not later than 7 days after the sponsor is first aware of the reaction. Any additional relevant information must be reported within a further 8 days;
- SUSARs that are not fatal or life-threatening must be reported within 15 days of the sponsor first becoming aware of the reaction.

The Chief Investigator and KHP-CTO (on behalf of the co-sponsors) will submit a Development Safety Update Report (DSUR) relating to this trial IMP, to the MHRA and REC annually.

10.3. Adverse events that do not require reporting

All adverse events will be reported from time of consent to final follow-up.

10.4. Premature Termination of the Trial

The trial may be prematurely discontinued by the Sponsor, Chief Investigator or Regulatory Authority on the basis of new safety information or for other reasons given by the trial's research team, regulatory authority or ethics committee concerned.

If the trial is prematurely discontinued, active participants will be informed, and no further participant data will be collected. The Competent Authority and REC will be informed within 15 days of the early termination of the trial. There are no pre-specified treatment-stopping rules.

Dosing Suspension Criteria

Dosing may be temporarily suspended (for the individual or all participants on decision by the Trial Steering Committee (TSC)) under any one of the following objective criteria: occurrence of any serious adverse event (SAE) related to the investigational medicinal product (IMP); observation of the same severe adverse reaction in two or more participants; or upon decision by the TSC or Chief Investigator based on safety concerns. Should dosing suspension occur, appropriate escalation procedures will be implemented, including implementation of Urgent

Safety Measures or major protocol amendments as deemed necessary by the regulatory and oversight framework.

11. Statistics

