5.5. Trial Flowchart

Table 1 Clinical Trial Plan by Visit

Procedure		Experimental visits ¹ F			Follow-up		
	Screening ≤ 28 days prior to IMP administratio n/Visit 1	Visit 1	Visit 2	Visit 3	Visit 4	Visit 5	7-14 days post-final visit (telephone/ online)
Written informed consent	X						
Demographic information ²	X						
Medical assessment ³	X						
Eligibility assessment/review	Х	Х	Х	Х	Х	Х	
Urine pregnancy test	X	Х	Х	Х	Х	Х	X8
Urine drug screen	X	Х	Х	Х	Х	Х	
Alcohol breath test	Х	Х	Х	Х	Х	Х	
IV cannulation		Х	Х	Х	Х	Х	
Blood sampling (FBC, LFTS, U&Es) ⁴	X						
Urinalysis ⁴	Х						
Vital signs ⁵	Х	Х	Х	Х	Х	Х	
ECG	X						
Randomisation		Х					
IMP administration ⁶		Х	Х	Х	Х	X	
Administration site check ¹¹		Х	Х	Х	Х	Х	
PK Sampling ⁷		Х	Х	Х	Х	Х	
Buccal Wafer Disintegration time ¹⁰		Х	Х	Х	Х	Х	
Visual Analogue Scale (VAS)		Х	Х	Х	Х	Х	
AE Review ⁹	•						
Conmed Review ⁹	4						—

Participants will be discharged on the same day as admission for each experimental visit.

- 1. Minimum 36 hrs between experimental visits. Breakdown of experimental visits in Section 8.1
- 2. Demographic information obtained will include sex, age, BMI, weight/height.
- 3. Includes review of pre-existing conditions, physical examination, medical, smoking, drug and alcohol history, and a conmed review of all medical products (incl. over-the-counter and herbal) 4. List in full in Section 8.3
- 5. Heart Rate (during experimental visit recorded via ECG), Respiratory Rate, Blood Pressure, Temperature, taken in supine position at specific timepoints in each experimental visit (pre-dose, 10 min, 30 min, 1 hr and 4hrs).
- 6. Five-way crossover design, in a randomised order for each participant on each study visit.
- 7. PK Sampling times detailed in Section 8.2.
- 8. WOCBP will be asked to confirm the result of a urine pregnancy test completed on that day, previously provided by the research team on the last dosing visit
- 9. All AEs and Conmed medications will be captured starting from the moment informed consent is obtained until the completion of follow-up. Adverse Event reviews to be conducted at screening, and specific timepoints during each experimental visit (pre-dose and 10 min, 30 min, 1 h and 4 h post IMP administration) and at follow-up (see Section 8.2)
- 10. Wafer disintegration time to be recorded for buccal/sublingual formulations only.
- 11. Administration site check at specific timepoints (pre-dose, 30 min and 4 hrs).

6. Trial Medication

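### Section 10.4 ends all participant data collection on early termination, which conflicts with the protocol's own safety follow-up of participants already dosed

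*Protocol*

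**What the plan says.** Section 10.4 (Premature Termination of the Trial) lets the sponsor, the chief investigator or the regulator end the trial "on the basis of new safety information or for other reasons given by the trial's research team", among others. It then gives the consequence for participants: "active participants will be informed, and no further participant data will be collected". The sentence carries no qualification.

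Other sections fix the safety observation period:

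- Section 10.3: "All adverse events will be reported from time of consent to final follow-up".
- Section 5.5, Table 1, footnote 9: "All AEs and Conmed medications will be captured starting from the moment informed consent is obtained until the completion of follow-up".
- Section 8.2.4: "The follow-up visit will be completed via remote video call (or phone call if video incapability) 7-14 days after the final dosing visit". At that contact, "Participants will be asked to report any adverse events" and "Female participants of childbearing potential will be asked to confirm the result of a urine pregnancy test completed on that day".
- Section 10.1 also lists a pregnancy test at the final follow-up visit, after those at screening and before each dosing session.

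**The concern.** The two sets of instructions cannot both be followed for a participant who has been dosed and is still awaiting the follow-up contact when the trial is terminated. Section 10.4 says to collect nothing more. Sections 10.3, 5.5 and 8.2.4 say to go on capturing adverse events and to make the contact. A site that takes 10.4 at its word would have grounds to cancel the call.

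Safety and tolerability of the wafer is a secondary objective (section 5.1), and the wafer is unlicensed (section 6.1.2). If a safety signal ended the trial, later reports from the most recently exposed participants would help to interpret it. Follow-up that is not done at the time cannot be recovered afterwards.

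This is not a detail that a protocol would leave to the statistical analysis plan. It is an explicit instruction in the safety section that disagrees with other explicit instructions.

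**Working it through.** No arithmetic applies to the contradiction itself. The check sets the rules side by side for one participant and then looks for any text that resolves the conflict.

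**One participant.** Call the day of the last dose received day 0.

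1. On day 0, adverse events are reviewed before dosing and at 10 minutes, 30 minutes, 1 hour and 4 hours (Table 1 footnote 9; section 8.2.2).
2. If another dosing visit follows, its pre-dose review covers the interval since the previous one. Earlier doses are therefore largely covered by later visits.
3. After the last dosing visit, the next scheduled enquiry is the follow-up contact, between day 7 and day 14 (section 8.2.4).
4. Suppose the trial is terminated after the 4-hour review on day 0 and before that contact. Under 10.3 and footnote 9, capture continues and the contact takes place. Under 10.4, nothing more is collected.
5. If the contact was completed before termination, nothing is lost.

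The data at stake are therefore the adverse-event enquiry for the interval from the last completed review to the contact, at most 14 days, and the pregnancy test at its end where it applies.

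**Does other text resolve the conflict?**

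- Section 7.6 (withdrawal) and section 17.2 (data management after early withdrawal) allow data already obtained to be kept. They neither forbid further collection nor restore follow-up after termination of the trial.
- The Urgent Safety Measures text in 10.4 belongs to temporary suspension of dosing, not to termination.
- Sections 10.2 and 10.2.1 require reporting of serious events within 24 hours, of unplanned pregnancies through the serious-event system, and of further information on fatal or life-threatening SUSARs within a further 8 days. Nothing in 10.4 withdraws these duties. They act on events that become known; they do not prompt a participant to report or to take a test. The 8-day duty also sits awkwardly with 10.4, because the further information may have to come from the participant.

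None of these provides an exception to the data-collection stop.

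**How many participants?** The answer needs the number dosed and awaiting follow-up on the day of termination. The protocol gives Stage 1 and Stage 2 sample sizes, but no recruitment rate and no figure for how many participants are in the study at once. The number cannot be derived.

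**The case against.** The best case against the point has four parts.

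- Section 10.4 never says that the follow-up call is cancelled. A sensible sponsor would probably make it anyway. This stands as far as it goes: the loss follows from the literal wording and is not announced as an intention.
- The reporting duties in 10.2 and 10.2.1 survive. This stands too. A reader might infer that all serious events and pregnancies would go unrecorded after a stop; the documents do not support that. What is exposed is the scheduled enquiry, which matters mainly for non-serious events, and the scheduled test.
- The clinical exposure is limited. Doses are single, section 6.2.1 gives a half-life under 2 hours, and each visit has repeated reviews. This reduces the likely loss but does not remove it: unresolved events, local effects at the administration site and pregnancies can still appear later.
- The conflict bites only on unplanned, permanent termination. Temporary suspension has its own rules in 10.4, to which the data-collection sentence is not attached. The planned stop after Stage 1 (section 5.4) is a design outcome based on completed Stage 1 data. This is correct and is why the point is not rated higher.

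A reader might also infer that most active participants, or nearly a whole stage, would be affected. At the shortest spacing, with sessions two days apart, five visits fall on days 1, 3, 5, 7 and 9, which is comparable with the 7-to-14-day wait. But that shows how long dosing can take, not how many people are waiting on a given day. Participation may also last up to about three months (section 6.2.1), and the number of Stage 2 visits is not yet decided (section 8.2.5). No head count is supported.

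**Conclusion.** The contradiction is real and nothing in the protocol resolves it. Its severity is moderate.

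The conclusion rests on reading 10.4 as written, and on a premature termination while some dosed participants have not had their follow-up contact. For each such participant, the scheduled adverse-event enquiry is at risk, as is the pregnancy test for women of childbearing potential. How many that would be is unknown.

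No endpoint, treatment-selection rule or planned analysis is affected if the trial runs to its designed end.

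**What to change.** Reconcile section 10.4 with Table 1 footnote 9 and sections 8.2.4, 10.1 and 10.3. The data-collection stop in 10.4 should be limited so that the safety follow-up already planned is exempt. Every participant who has received any dose would then still have the adverse-event enquiry and, where applicable, the pregnancy test, subject to consent.

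It would help to say that, after an early stop, the timing of the contact counts from the last dosing visit actually attended. Section 8.2.4 has the pregnancy test handed over at the last dosing visit, so a participant stopped before the planned final visit may need to be sent one.

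Sections 7.6 and 17.2 need no change, because neither forbids further collection. No rule on dosing is proposed.

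The cost is about one sentence in an amendment, a remote call that is already planned for each participant, and possibly a few posted test kits.

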11.1. Sample Size

No formal sample size calculation is computed as this is a pharmacokinetic study. Treatment selection will be made based on complete data of 12 participants (with five responses from each participant, each for an arm) at stage 1. With an expected drop-out rate of 20%, we expect to randomise 15 participants. This sample size exceeds the EMA recommendations for minimum sample size in pharmacokinetic studies for comparing formulations, providing robust data for analysis.

Stage 2 will recruit 30-35 participants, depending on the dropout rate observed in stage 1. A cross-over design will be implemented in stage 2 where the number of arms depend on the findings from stage 1. Participants that partake in stage 1 will not be eligible to also participate in Stage 2.

